10.6 Stopping rules

The trial will be stopped if at interim data analysis there is a highly significant difference (p<0.001) between the tamsulosin group and the placebo group in the primary outcome. Data monitoring will be performed by the ICTR DMC every 6-12 months as needed. The single planned interim data analysis will be performed between May 15 and May 30, 2016, by the PI ([name]), [name], [name], and [name] for the purposes of a Master's thesis project. If the rate of either priapism or syncope in the tamsulosin group exceeds that of the placebo group by an absolute value of 10%, then the study will be stopped.

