In the two U.S. clinical trials referenced above, symptomatic postural hypotension occurred in 0.2% of men treated with tamsulosin 0.4mg vs. no patients in the placebo groups. Syncope occurred in 0.2% of men treated with tamsulosin 0.4mg vs. 0.6% in the placebo groups. Multiple testing for orthostatic hypotension was also performed in these studies, and demonstrated a 16% rate of at least one positive orthostatic test result in the tamsulosin 0.4mg subjects, vs. 11% rate in the placebo group.^{7,8}

No men in the tamsulosin 0.4mg group or placebo group discontinued treatment due to abnormal ejaculation.

In a double-blind RCT comparing tamsulosin 0.2mg to placebo in 140 women over a 4-week period, there were 2 patients out of 70 in the tamsulosin group who had dizziness and asthenia (2.9%) compared to no adverse effects reported in the placebo group.⁹

- 9.1.10.1 Incidence not known (Post-marketing experience)
 - 9.1.10.1.1 Allergic reactions including skin rash, pruritus, angioedema of tongue, lips and face, urticarial. This has been reported in patients with severe sulfa allergy, and therefore severe sulfa allergy is one of the exclusion criteria for this study.
 - 9.1.10.1.2 skin desquamation
 - 9.1.10.1.3 Priapism (probably less than 1 in 50,000 patients)
 - 9.1.10.1.4 palpitations
 - 9.1.10.1.5 hypotension
 - 9.1.10.1.6 constipation
 - 9.1.10.1.7 vomiting
 - 9.1.10.1.8 Intraoperative Floppy Iris Syndrome (IFIS): This is a clinical syndrome of a flaccid billowing iris, iris prolapse, and pupil constriction that has been described during cataract surgery and has been associated with tamsulosin. This syndrome increases the difficulty of performing cataract surgery and increases the rate of complications associated with cataract surgery.¹⁰ It has been found to occur even up to a year after discontinuation of tamsulosin, and possibly longer.¹¹ However, one prospective study evaluating outcomes after surgery in which IFIS was present found that when surgeons were aware of prior or current tamsulosin use, they were able to employ compensatory techniques resulting in a low complication rate.¹¹

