13.1 Data Monitoring Committee

We plan to utilize the UW ICTR Data Monitoring Committee (DMC) to oversee the study. The UW ICTR DMC is co-chaired by [name] and [name] and is comprised of experienced members (core plus ad hoc) with expertise required to oversee this study. The DMC members will review protocol-specific reports created by statisticians using data pulled from the ICTR OnCore clinical research management system. These standard reports will include an overview of study objectives, a review of actual and projected accrual rates, an evaluation of patient demographics for balance of randomization, and a summary of the number and seriousness of adverse events. An interim analysis of study results may be performed and source documents may be reviewed to allow the DMC to independently judge whether the overall integrity and conduct of the protocol remain acceptable based on data provided and reported by the Principal Investigator. The DMC will make recommendations to the Principal Investigator that could include actions of continuation, modification or termination.

In providing oversight for the conduct of this study, the ICTR DMC will meet every 6 months during the 3-year study to review all adverse events. The predefined stopping points for this study will include excess rates of syncope, or priapism requiring medical treatment. The boundary for excess harm will be an incidence of syncope or priapism in the tamsulosin group that exceeds that of the placebo group by an absolute value of 5%, or an observed excess harm which in the judgment of the DMC, is excessive. We will report all serious adverse events to the DMC and the IRB oversight committee, the Health Sciences IRB in accordance with their reporting guidelines.

The individuals responsible for data and safety monitoring are independent of the researchers.

If a subject prematurely withdraws from the study, then a study team member will call the patient (or visit the patient in the hospital) to inquire about adverse events.

Between May 15-30, 2016, unblinding will occur for subjects for which complete data collection (30 days from operation) has been achieved, and interim data analysis will then be performed by [name] (the PI), [name], [name], and [name] for purposes of a Master's research project.

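### The harm-stopping threshold for syncope or priapism is a 10-point excess in section 10.6 but a 5-point excess (or DMC judgment) in section 13.1, and nothing says which governs

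*Combined protocol and SAP*

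**What the plan says.** Section 10.6 (Stopping rules) orders the study stopped on a between-arm excess of either event: "If the rate of either priapism or syncope in the tamsulosin group exceeds that of the placebo group by an absolute value of 10" percent. It says nothing about what follows from a smaller excess.

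Section 13.1 (Data Monitoring Committee) also presents its limits as stopping points: "The predefined stopping points for this study will include excess rates of syncope, or priapism requiring medical treatment". It then sets the boundary as an incidence on tamsulosin above the one on placebo "by an absolute value of 5%, or an observed excess harm which in the judgment of the DMC, is excessive". The committee is advisory: "The DMC will make recommendations to the Principal Investigator that could include actions of continuation, modification or termination".

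The event definition also varies slightly. Section 13.1 introduces the stopping point as "excess rates of syncope, or priapism requiring medical treatment", while its own boundary sentence and section 10.6 say only priapism.

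For background rates, section 9.1.10 (Side effects) reports from two trials in men with prostatic hypertrophy: "Syncope occurred in 0.2% of men treated with tamsulosin 0.4mg vs. 0.6% in the placebo groups". The post-marketing list in 9.1.10.1 gives "Priapism (probably less than 1 in 50,000 patients").

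**The concern.** The two sections describe one rule: same events, same contrast (tamsulosin minus placebo), same absolute scale. The numbers differ by a factor of two. A reader who goes to the section headed as stopping rules finds only 10%; a reader of the DMC section finds only 5%.

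A boundary is fixed in advance so that nobody has to argue, with unblinded data in hand, about whether it has been met. Here an excess between 5 and 10 points crosses the boundary in 13.1 and does not trigger 10.6. The DMC could recommend termination citing its own section, and the investigator who receives that advice could reply that the stopping rule in 10.6 has not been met. Each would be relying on current protocol text.

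**Working it through.** **Text comparison.** This settles the point.

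| | Section 10.6 | Section 13.1 |
|---|---|---|
| Events | priapism or syncope | syncope or priapism (introduced as priapism needing treatment) |
| Contrast | tamsulosin minus placebo | tamsulosin minus placebo |
| Threshold | more than 10 points | more than 5 points, or DMC judgment |
| Consequence | study is stopped | predefined stopping point; DMC recommends to the investigator |
| Reference to the other section | none | none |

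Neither threshold is derived from anything in the plan, so there is no plan calculation to reproduce. The arithmetic below only sizes the gap.

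**Inputs.** Allocation is 1:1 (10.1), with 134 per arm for analysis and 147 per arm to be enrolled (10.2). The 134 reproduces from 30% against 15%, two-sided 0.05 and 80% power with a continuity correction (121 without it). Accrual is 1 to 2 subjects per week (10.5). Syncope is 0.2% on tamsulosin and 0.6% on placebo (9.1.10). All other rates are assumptions, as are the looks at 13, 26 and 67 per arm.

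**Events needed to cross.** With n per arm and threshold d, the smallest excess count that exceeds the threshold is k = floor(n × d) + 1.

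| n per arm | k, 5% rule | k, 10% rule | Excess in dispute |
|---|---|---|---|
| 13 | 1 | 2 | 1 |
| 67 | 4 | 7 | 4 to 6 |
| 134 | 7 | 14 | 7 to 13 |
| 147 | 8 | 15 | 8 to 14 |

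For example, at 134 per arm 0.05 × 134 = 6.7, so k = 7 (7/134 = 5.2%), and 0.10 × 134 = 13.4, so k = 14 (14/134 = 10.4%).

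One unmatched event exceeds 5% whenever 1/n > 0.05, that is up to 19 per arm. It exceeds 10% only up to 9 per arm.

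**Chance of crossing at a single look.** Let T and C be independent binomial counts on tamsulosin and placebo. Then P(cross) = Σ over c of P(C = c) × P(T ≥ c + k), by exact enumeration.

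| n per arm | Tamsulosin vs placebo | 5% rule | 10% rule |
|---|---|---|---|
| 134 | 0.2% vs 0.6% (documented) | 6 × 10⁻⁹ | essentially 0 |
| 134 | 1% vs 0.6% | 0.02% | essentially 0 |
| 134 | 2% vs 0.6% | 1.1% | 0.00003% |
| 134 | 3% vs 0.6% | 7.0% | 0.003% |
| 134 | 5% vs 0.6% | 39% | 0.5% |
| 134 | 6% vs 1% | 51% | 1.5% |
| 134 | 8% vs 1% | 80% | 11% |
| 67 | 0.2% vs 0.6% (documented) | 7 × 10⁻⁶ | essentially 0 |
| 67 | 3% vs 0.6% | 11% | 0.3% |
| 13 | 0.2% vs 0.6% (documented) | 2.4% | 0.03% |
| 26 | 0.2% vs 0.6% (documented) | 0.1% | 0.002% |

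The rows at 13 and 26 per arm are a first six-month review at 1 and at 2 subjects per week (26 or 52 subjects in 26 weeks, all assumed evaluable). At 13 per arm one unmatched syncope is 1/13 = 7.7%, above 5% and below 10%. At 26 it is 1/26 = 3.8% and crosses neither.

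At under 1 in 50,000 for priapism, any dispute will in practice concern syncope.

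**The case against.** The strongest reply is that the two rules can be obeyed together. Section 10.6 gives a condition that is sufficient for stopping; it does not order continuation below 10%. Any excess above 10 points is also above 5, so following 13.1 satisfies 10.6, and the DMC may recommend termination at any excess. This is right, and it is why the risk to subjects is limited. It does not say which fixed number governs. A two-tier reading (5% for a recommendation, 10% for a mandatory stop) is plausible, but the plan does not state it, and 13.1 calls its own limits stopping points.

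Second, the study team is blinded apart from the single 2016 interim, whose result section 10.5 already reports, so only the DMC could see an excess by arm. That narrows the room for dispute. It does not remove it, because the DMC's advice goes to the investigator.

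Third, the size is easy to overstate. At 134 per arm accrual is essentially complete and there is little left to stop. The large probabilities need syncope of 5% to 8% on tamsulosin, 25 to 40 times the documented 0.2%. The small early review is probably past: from the end of May 2016 to this version (December 8, 2017) is about 80 weeks, which at one subject per week adds about 40 per arm. All of this stands and lowers the practical consequence. Against it, the documented rates come from men with prostatic hypertrophy, while this trial enrols men and women having major abdominal surgery, so the relevant syncope rate is unknown.

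**Conclusion.** The concern holds, and it should be fixed. The current text gives two values for one safety threshold, and nothing in the plan reconciles them. That conclusion rests on the wording alone and needs no assumption about rates.

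The practical effect is probably small. If syncope runs near the documented rates, a crossing at mid-trial or later is very unlikely under either rule. It becomes material only if syncope on tamsulosin in this surgical population is several percentage points above placebo, which the documents neither support nor exclude. In that range the choice of rule largely decides whether a predefined boundary is reached.

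**What to change.** State one threshold in both sections and confirm it with the DMC. The default is to replace the 10% in section 10.6 with the boundary in 13.1 (an absolute excess above 5%, or DMC judgment) and have 10.6 refer to 13.1. The stricter rule is the safer default because meeting it also meets 10.6. If two tiers were intended, write them out: 5% prompts a DMC recommendation, 10% is a mandatory stop.

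In the same edit, use one definition of the priapism event throughout, and align the DMC review interval, which is 6 to 12 months as needed in 10.6 and 6 months in 13.1.

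The cost is protocol wording and the DMC's agreement; no new data or subjects are needed. The trade-off is a somewhat higher chance of an early safety stop, including on one unmatched event at any review with 19 or fewer subjects per arm.

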10.5 Estimated accrual rate / study duration

The estimated sample size needed to achieve the pre-specified statistical significance and power is a total of 268 subjects (134 subjects in each arm). Subjects that withdraw from the study prior to surgery will be replaced. We estimate that there will be a 10% drop-out rate, and therefore the enrollment goal to account for drop-outs is estimated to be 294 subjects (147 in each arm) in order to achieve an actual sample size of 268 subjects. We initially predicted that we would need to replace subjects that received epidural anesthesia, but the interim analysis showed no significant difference in response between epidural and non-epidural patients.

The estimated accrual rate is approximately 1-2 subjects per week. In order to enroll a total of 294 subjects, this would take approximately 147-294 weeks, or 2.8-5.7 years. After enrollment of the final subject, data collection will continue for 30 days beyond that subject's date of surgery. Expected study duration is approximately 3-6 years from the time that enrollment begins.

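### Sections 10.6 and 13.1 set different stopping thresholds, 10 and 5 percentage points, for the same excess of priapism or syncope on tamsulosin

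*Combined protocol and SAP*

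**What the plan says.** Section 10.6 gives the rule as "If the rate of either priapism or syncope in the tamsulosin group exceeds that of the placebo group by an absolute value of 10" percent, and the consequence is that the study stops.

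Section 13.1 introduces its own predefined stopping points as "excess rates of syncope, or priapism requiring medical treatment". The next sentence supplies the number. Its trigger is a rate of either event on the active drug which "exceeds that of the placebo group by an absolute value of 5%, or an observed excess harm which in the judgment of the DMC"; the second limb leaves the DMC free to find a smaller excess too large. The same section says that "the ICTR DMC will meet every 6 months during the 3-year study to review all adverse events". Section 10.6 describes DMC monitoring as every 6 to 12 months, as needed.

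The denominators come from section 10.2: 134 evaluable per arm, and 147 per arm as the enrollment goal, with 1:1 allocation (10.1). On accrual, section 10.5 says: "The estimated accrual rate is approximately 1-2 subjects per week". The only background syncope figures are in the side-effect text of section 9.1.10, from two US trials in men: "Syncope occurred in 0.2% of men treated with tamsulosin 0.4mg vs. 0.6% in the placebo groups".

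**The concern.** A harm stopping rule should give one answer for one set of data. Here the events, the arms compared and the absolute scale are the same, and the thresholds differ by a factor of two. For an observed excess between 5 and 10 points, someone working from 13.1 would find the boundary crossed, and someone working from 10.6 would not. The disagreement would surface when an unexpected safety signal is being discussed, which is a poor time to settle which sentence was meant. What is at stake is how clearly the trial responds to harm. The primary efficacy analysis is not involved.

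**Working it through.** **1. The plan's denominator.** Inputs from 10.2 and 10.3: 30% versus 15%, two-sided alpha 0.05, power 80%.

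- Without continuity correction: n = [1.96·√(2·0.225·0.775) + 0.842·√(0.30·0.70 + 0.15·0.85)]² / 0.15² = 120.5, so 121 per arm.
- With continuity correction: (120.5/4)·[1 + √(1 + 4/(120.5·0.15))]² = 133.5, so 134 per arm. This matches the plan.
- The plan's 10% allowance: 134 × 1.10 = 147.4, given as 147.

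The two harm thresholds have no stated derivation, so there is nothing to reproduce for them.

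**2. Thresholds as case counts.** With equal arms, the smallest crossing count is the smallest whole net excess (tamsulosin minus placebo) above threshold × n.

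| n per arm | 5% × n | Cases to cross 13.1 | 10% × n | Cases to cross 10.6 | Sections disagree at |
|---|---|---|---|---|---|
| 50 | 2.5 | 3 | 5.0 | 6 | 3 to 5 |
| 67 | 3.35 | 4 | 6.7 | 7 | 4 to 6 |
| 134 | 6.7 | 7 (5.2%) | 13.4 | 14 (10.4%) | 7 to 13 |
| 147 | 7.35 | 8 (5.4%) | 14.7 | 15 (10.2%) | 8 to 14 |

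**3. How much the choice matters if harm is real.** For a single look at 134 per arm, the crossing probability is the sum of Bin(x; 134, p_T)·Bin(y; 134, p_C) over all x − y > d·134. The true rates below are assumptions for illustration.

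- 8% versus 0.5%: 0.87 under the 5-point rule, 0.14 under the 10-point rule.
- 3% versus 0%: 0.11 under the 5-point rule, below 0.001 under the 10-point rule.

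**4. How often each rule is crossed with no true harm.** The difference in case counts is carried exactly from look to look, and a trial counts as crossed at the first look where difference / n exceeds the threshold. Assumptions: equal syncope rates in both arms; everyone randomised by a look has been observed; 6-month looks. At 1 subject per week, looks fall every 26/2 = 13 per arm, up to 130.

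| Equal syncope rate | Looks counted (per arm) | 5-point | 10-point |
|---|---|---|---|
| 0.6% | 52, 65, …, 130 | 0.3% | below 0.01% |
| 0.6% | 65, 78, …, 130 | 0.1% | below 0.01% |
| 2% (assumed) | 52, 65, …, 130 | 4.9% | 0.03% |
| 0.6% | 13, 26, …, 130 | 7.8% | 0.27% |
| 0.6% (2 subjects per week) | 26, 52, …, 130 | 1.1% | 0.04% |

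In the fourth row, 7.0 of the 7.8 points arise at the 13-per-arm look, where one net case is enough (1/13 = 7.7%).

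**5. Which looks still lie ahead.** The text is Version 5.0, December 8, 2017, and 10.5 reports the interim analysis (planned for May 15–30, 2016) as done. From the end of May 2016 to that date is about 79 weeks. At 1–2 subjects per week this adds about 40 to 79 per arm (79 × 1/2 to 79 × 2/2) to those enrolled earlier. Starting at 52 per arm is therefore a reasonable assumption for the remaining looks, but the documents give no actual enrollment count.

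**The case against.** **The two figures could be tiers: review at 5 points, stop at 10.** That would be a sensible design, but no text describes it. Section 13.1 calls its own events predefined stopping points, the same function as the heading of 10.6.

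**The rules are unlikely ever to disagree.** This has force. At 0.6%, about 0.8 syncope cases are expected per arm (0.006 × 134), far from a net excess of 7 to 13. In addition, 13.1 has the DMC review all adverse events and lets it act below the numerical boundary. This limits the practical effect. It does not settle which number applies, and the 0.6% comes from men in earlier tamsulosin trials, whereas this trial enrolls adults of either sex having major abdominal surgery.

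**Stronger readings that a reader might infer, and that the documents do not support:**

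- *That the consequences also conflict, with a mandatory stop in 10.6 and only advice in 13.1.* The sentence "The DMC will make recommendations to the Principal Investigator that could include actions of continuation, modification or termination" belongs to the general paragraph on DMC duties. Section 13.1 does not say that crossing this boundary leads only to a recommendation.
- *That the 5-point rule carries a false-crossing rate near 8% and so needs an exemption for small numbers.* Most of that figure comes from a 13-per-arm look that has very likely passed. It also depends on six-monthly looks: with 12-month looks at 1 subject per week it is 1.1%.
- *That priapism is defined inconsistently.* The qualifier about medical treatment stands in the sentence just before the boundary and can be read as carrying over. Syncope has no such difference, so the conflict stands on syncope alone.

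**Conclusion.** The inconsistency is real and stands in current text. Sections 10.6 and 13.1 give 10 and 5 points for the same harm comparison, and nothing ranks them. Its size is a net excess of 7 to 13 cases at 134 per arm, or 8 to 14 at 147, for which the two sections give different answers. That count needs only equal arm sizes. The chance-crossing figures rest on more: an assumed common syncope rate, the look schedule, and an assumed 52 or more per arm already enrolled.

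This is worth correcting but is no more than a modest point. A reader might infer that participants are left without protection between 5 and 10 points. The documents do not support that, given the DMC's review of adverse events and its freedom to act on judgment. Sample size and the primary test are unaffected.

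**What to change.** In 10.6, replace the 10 percent figure with the 13.1 boundary (an excess above 5 percentage points, or excess harm in the judgment of the DMC), or replace the sentence with a cross-reference to 13.1, so that one threshold applies. The 5-point figure is the more protective one and sits in the section that governs the DMC. Optionally, repeat the qualifier about medical treatment for priapism in both places. Reconciling the sections does not require a change to what follows a crossing, or a small-sample exemption.

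The cost is a sentence or two of wording, with no new data. The downside is a somewhat higher chance of crossing without true harm: about 0.3% or less from 52 per arm onward at an equal 0.6% syncope rate, and more if background syncope is higher (4.9% at an assumed 2%) or if looks occur at very small numbers.

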10.7 Primary endpoint for interim and final analysis

The primary endpoint for interim and final analysis is need for any intermittent catheterization after initial IUC removal. This outcome will be compared primarily with an intent-to-treat analysis. However, we will also perform an as-treated analysis. Compliance will be measured based on pill-counts. A subject will be considered "compliant" if greater than or equal to 70% of the pills that were supposed to be taken were actually taken.

10.8 Hypotheses

10.8.1 Primary

10.8.1.1 We hypothesize that subjects treated with tamsulosin will have a decreased need for intermittent catheterization after initial IUC removal compared to those treated with placebo.

10.8.2 Secondary

10.8.2.1 Subjects treated with tamsulosin will have a lower rate of IUC replacement compared to those treated with placebo.

- 10.8.2.2 Subjects treated with tamsulosin will have a higher incidence of abnormal ejaculation, dizziness, and orthostasis compared to those treated with placebo.
- 10.8.2.3 Subjects treated with tamsulosin will have a shorter time until first spontaneous void compared to those treated with placebo.
- 10.8.2.4 Subjects treated with tamsulosin will have a fewer number of total intermittent catheterizations required per subject compared to those treated with placebo.
- 10.8.2.5 The tamsulosin group will have a smaller average post void residual urine volume after first spontaneous void compared to the placebo group.
- 10.8.2.6 The tamsulosin group will have a smaller proportion of patients being discharged from the hospital with an IUC compared to the placebo group.
- 10.8.2.7 The tamsulosin group will have a lower incidence of urinary tract infection diagnosed within 30 days of operation compared to the placebo group.
- 10.8.2.8 Subjects treated with tamsulosin will have a shorter average hospital length of stay (in days) compared to those treated with placebo.
- 10.8.2.9 Male gender, high preoperative IPSS score, older age, pelvic operations, larger volume of intraoperative fluids, and epidural anesthesia will be risk factors for POUR.
- 10.8.2.10 Higher risk patient groups will be most likely to benefit from tamsulosin therapy for the prevention of POUR.

